#### **8.4.1 Time Period and Frequency for Collecting AE, SAE, and Other Reportable Safety Event Information**

All AEs, SAEs, and other reportable safety events that occur after the consent form is signed but before treatment allocation/randomization must be reported by the investigator if the participant is receiving placebo run-in or other run-in treatment, if the event cause the participant to be excluded from the study, or is the result of a protocol-specified intervention, including but not limited to washout or discontinuation of usual therapy, diet, or a procedure.

- All AEs from the time of treatment allocation/randomization through 30 days following cessation of study intervention must be reported by the investigator.
- All AEs meeting serious criteria, from the time of treatment allocation/randomization through 90 days following cessation of study intervention or 30 days following cessation of study intervention if the participant initiates new anticancer therapy, whichever is earlier, must be reported by the investigator.
- All pregnancies and exposure during breastfeeding, from the time of treatment allocation/randomization through 120 days following cessation of study intervention, or 30 days following cessation of study intervention if the participant initiates new anticancer therapy must be reported by the investigator.
- Additionally, any SAE brought to the attention of an investigator at any time outside of the time period specified above must be reported immediately to the Sponsor if the event is considered drug-related.

Investigators are not obligated to actively seek AE or SAE or other reportable safety events in former study participants. However, if the investigator learns of any SAE, including a death, at any time after a participant has been discharged from the study, and he/she considers the event to be reasonably related to the study intervention or study participation, the investigator must promptly notify the Sponsor.

All initial and follow-up AEs, SAEs, and other reportable safety events will be recorded and reported to the Sponsor or designee within the time frames as indicated in [Table 9](#).

Table 9 Reporting Time Periods and Time Frames for Adverse Events and Other Reportable Safety Events

Type of Event	Reporting Time Period: Consent to Randomization/ Allocation	Reporting Time Period: Randomization/ Allocation through Protocol-Specified Follow-up Period	Reporting Time Period: After the Protocol Specified Follow-up Period	Timeframe to Report Event and Follow-up Information to Sponsor:
Non-Serious Adverse Event (NSAE)	Report if: - due to protocol-specified intervention - causes exclusion - participant is receiving placebo run-in or other run-in treatment	Report all	Not required	Per data entry guidelines
Serious Adverse Event (SAE) including Cancer and Overdose	Report if: - due to protocol-specified intervention - causes exclusion - participant is receiving placebo run-in or other run-in treatment	Report all	Report if: drug-/vaccine-related. (Follow ongoing to outcome)	Within 24 hours of learning of event
Pregnancy/Lactation Exposure	Report if: - due to intervention - causes exclusion	Report all	Previously reported – Follow to completion/termination; report outcome	Within 24 hours of learning of event
Event of Clinical Interest (require regulatory reporting)	Report if: - due to intervention - causes exclusion	Report - Potential drug-induced liver injury (DILI) - Require regulatory reporting	Not required	Within 24 hours of learning of event
Event of Clinical Interest (Do not require regulatory reporting)	Report if: - due to intervention - causes exclusion	Report - non-DILI ECIs and those not requiring regulatory reporting	Not required	Within 5 calendar days of learning of event

#### **8.4.2 Method of Detecting AEs, SAEs, and Other Reportable Safety Events**

Care will be taken not to introduce bias when detecting AE and/or SAE and other reportable safety events. Open-ended and nonleading verbal questioning of the participant is the preferred method to inquire about AE occurrence.

#### **8.4.3 Follow-up of AE, SAE, and Other Reportable Safety Event Information**

After the initial AE/SAE report, the investigator is required to proactively follow each participant at subsequent visits/contacts. All AE, SAE, and other reportable safety events including pregnancy and exposure during breastfeeding, events of clinical interest (ECI), cancer, and overdose will be followed until resolution, stabilization, until the event is otherwise explained, or the participant is lost to follow-up (as defined in Section 7.3). In addition, the investigator will make every attempt to follow all nonserious AEs that occur in randomized participants for outcome. Further information on follow-up procedures is given in Appendix 3.

#### **8.4.4 Regulatory Reporting Requirements for SAE**

Prompt notification (within 24 hours) by the investigator to the Sponsor of SAE is essential so that legal obligations and ethical responsibilities towards the safety of participants and the safety of a study intervention under clinical investigation are met.

The Sponsor has a legal responsibility to notify both the local regulatory authority and other regulatory agencies about the safety of a study intervention under clinical investigation. All AEs will be reported to regulatory authorities, IRB/IECs, and investigators in accordance with all applicable global laws and regulations (ie, per ICH Topic E6 (R2) Guidelines for Good Clinical Practice [GCP]).

Investigator safety reports must be prepared for suspected unexpected serious adverse reactions (SUSARs) according to local regulatory requirements and Sponsor policy and forwarded to investigators as necessary.

An investigator who receives an investigator safety report describing an SAE or other specific safety information (eg, summary or listing of SAE) from the Sponsor will file it along with the IB and will notify the IRB/IEC, if appropriate according to local requirements.

#### **8.4.5 Pregnancy and Exposure During Breastfeeding**

Although pregnancy and infant exposure during breastfeeding are not considered AEs, any pregnancy or infant exposure during breastfeeding in a participant (spontaneously reported to the investigator or their designee), including the pregnancy of a male participant's female partner, that occurs during the study are reportable to the Sponsor.

All reported pregnancies must be followed to the completion/termination of the pregnancy. Pregnancy outcomes of spontaneous abortion, missed abortion, benign hydatidiform mole, blighted ovum, fetal death, intrauterine death, miscarriage, and stillbirth must be reported as

serious events (Important Medical Events). If the pregnancy continues to term, the outcome (health of infant) must also be reported.

#### **8.4.6 Disease-related Events and/or Disease-related Outcomes Not Qualifying as AEs or SAEs**

Progression of the cancer under study is not considered a reportable event unless it results in hospitalization or death.

#### **8.4.7 Events of Clinical Interest (ECIs)**

Selected nonserious and SAEs are also known as ECIs and must be reported to the Sponsor.

Events of clinical interest for this study include:

1. An overdose of Sponsor's product, as defined in Section 8.5, that is not associated with clinical symptoms or abnormal laboratory results.
2. An elevated AST or ALT lab value that is greater than or equal to 3X the upper limit of normal and an elevated total bilirubin lab value that is greater than or equal to 2X the upper limit of normal and, at the same time, an alkaline phosphatase lab value that is less than 2X the upper limit of normal, as determined by way of protocol-specified laboratory testing or unscheduled laboratory testing.\*

\*Note: These criteria are based upon available regulatory guidance documents. The purpose of the criteria is to specify a threshold of abnormal hepatic tests that must trigger an additional evaluation for an underlying etiology. The study site guidance for assessment and follow up of these criteria can be found in the Investigator Study File Binder (or equivalent).

#### **8.4.8 Medical Device Incidents (Including Malfunctions)**

Not applicable.

#### **8.5 Treatment of Overdose**

For this study, an overdose of pembrolizumab will be defined as any dose of 1000 mg or greater.

No specific information is available on the treatment of overdose of pembrolizumab. In the event of overdose, the participant should be observed closely for signs of toxicity. Appropriate supportive treatment should be provided if clinically indicated.

#### **8.6 Pharmacokinetics**

To evaluate pembrolizumab immunogenicity and pembrolizumab exposure after MK-3475 SC administration (Cohort A ), and Q6W dosing (Cohort B), sample collections for analysis

of ADAs and PK are currently planned as shown in the SoA (Section 1.3). Blood samples will be obtained to measure PK of serum pembrolizumab. The pembrolizumab serum concentration at planned visits and times will be summarized.

### **8.6.1 Blood Collection for Plasma for Pembrolizumab Pharmacokinetics and Immunogenicity**

Sample collection, storage, and shipment instructions for plasma samples will be provided in the procedures/laboratory manual.

#### **8.6.1.1 Blood Collection for Pharmacokinetics**

Sample collection, storage, and shipment instructions for serum samples will be provided in the procedure/laboratory manual. Pharmacokinetic samples should be drawn according to the PK collection schedule for all participants.

#### **8.6.1.2 Blood Collection for Anti-pembrolizumab Antibodies**

Sample collection, storage, and shipment instructions for serum samples will be provided in the procedure manual. Anti-pembrolizumab antibody samples should be drawn according to the ADA collection schedule for all participants (Section 1.3).

### **8.7 Pharmacodynamics**

Pharmacodynamic parameters will not be evaluated in this study.

### **8.8 Future Biomedical Research Sample Collection**

Future biomedical research samples will not be collected in this study.

### **8.9 Planned Genetic Analysis Sample Collection**

Planned genetic analysis samples will not be evaluated in this study.

### **8.10 Biomarkers**

Biomarkers are not evaluated in this study.

#### **8.10.1 RNA Transcriptome Research**

Not applicable.

#### **8.10.2 RNA Expression Research of a Subset of RNA Species**

Not applicable.

### **8.10.3 Proteome Research**

Not applicable.

### **8.10.4 Metabolomic Research**

Not applicable.

## **8.11 Visit Requirements**

Visit requirements are outlined in Section 1.3. Specific procedure-related details are provided in Section 8.

### **8.11.1 Screening**

Written consent must be obtained prior to performing any protocol-specific procedure. Results of a test performed prior to the participant signing consent as part of routine clinical management are acceptable in lieu of a screening test if performed within the specified time frame. Screening procedures are to be completed within 28 days prior to the first dose of study intervention except for the following:

- Laboratory tests are to be performed within 72 hours prior to the first dose of study intervention. An exception is hepatitis and thyroid testing which may be done up to 28 days prior to the first dose of study intervention.
- Evaluation of ECOG is to be performed within 7 days prior to the first dose of study intervention.
- For women of reproductive potential, a urine or serum pregnancy test will be performed within 72 hours prior to the first dose of study intervention. If urine pregnancy results cannot be confirmed as negative, a serum pregnancy test will be required (performed by the local study site laboratory).

Participants may be rescreened after initially failing to meet the inclusion/exclusion criteria. Results from assessments during the initial screening period are acceptable in lieu of a repeat screening test if performed within the specified time frame and the corresponding inclusion/exclusion criteria is met. Participants who are rescreened will retain their original screening number.

### **8.11.2 Treatment Period**

Visit requirements are outlined in the SoA (Section 1.3). Specific procedure-related details are provided in Section 8.1.

### **8.11.3 Discontinued Participants Continuing to be Monitored in the Study**

The End of Treatment visit should occur at the time study treatment is discontinued for any reason. Visit requirements are outlined in the SoA (Section 1.3).

If the End of Treatment visit occurs 30 days from the last dose of study treatment, at the time of the mandatory Safety follow-up visit, the End of Treatment visit procedures and any additional safety follow up procedures should be performed.

#### **8.11.3.1 Follow-up Visits**

##### **Cohort B**

Participants who discontinue study treatment for a reason other than disease progression will move into the Follow-Up Phase and should be assessed every 12 weeks ([84] days  $\pm$  7 days) to monitor disease status. Every effort should be made to collect information regarding disease status until the start of new anti-cancer therapy, disease progression, death, end of study.

#### **8.11.3.2 Safety Follow-up Visit**

Participants will be required to return to the clinic for the Safety follow-up visit approximately 30 days after the last dose of study treatment or before initiating a new anticancer therapy, whichever occurs first. If the Safety follow-up visit occurs less than 30 days after the last dose of study treatment, a subsequent follow up phone call should be made 30 calendar days after the last dose of study treatment to determine if any AEs occurred since the last study visit.

After treatment discontinuation, participants will be monitored for AEs for 30 calendar days and SAEs for 90 calendar days after the last administration of the investigational product (30 calendar days if the participant initiates new anticancer therapy). Participants with an ongoing AE at the time of treatment discontinuation will be followed until resolution, stabilization, the event is otherwise explained, or the participant is lost to follow-up.

If the End of Treatment visit occurs 30 days from the last dose of study treatment, at the time of the mandatory Safety follow-up visit, the End of Treatment visit procedures and any additional safety follow up procedures should be performed.

### **8.11.3.3 Survival Follow-up**

#### **Cohort A**

Survival follow-up will not be collected for participants in Cohort A.

#### **Cohort B**

Participants who experience confirmed disease progression or start a new anticancer therapy, will move into the Survival follow-Up Phase and should be contacted by telephone approximately every 12 weeks to assess for survival status until death, withdrawal of consent, or the end of the trial, whichever occurs first.

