	Arm 7	Pembrolizumab	25 mg/mL/ 400 mg	Q6W	IV	Day 1 of each 42-day cycle	Experimental	
	IV=intravenous; Q3W=every 3 weeks; Q6W=every 6 weeks; SC=subcutaneous.							

Total Number	Cohort A: 6 Arms Cohort B: 1 Arm
Duration of Participation	
Each participant will participate in the study from the time the participant signs the Informed Consent Form through the final protocol-specified contact.
 
After a screening phase of up to 28 days, each participant will be assigned to receive study treatment until disease progression is radiographically documented, confirmed by the site per modified Response Evaluation Criteria in Solid Tumors 1.1 (iRECIST) when clinically appropriate, unacceptable AEs, intercurrent illness that prevents further administration of treatment, investigator’s decision to discontinue the participant, noncompliance with study treatment or procedure requirements or administrative reasons requiring cessation of treatment, or until the participant has received 35 administrations (Cohort A) or 18 administrations (Cohort B) of pembrolizumab (approximately 2 years).
 
After the end of treatment, each participant will be followed for the occurrence of AEs and spontaneously reported pregnancy as described under Section 8.4.
 
In Cohort B participants who discontinue for reasons other than radiographic disease progression will have post-treatment follow-up imaging for disease status until disease progression is documented radiographically per RECIST 1.1, and, when clinically appropriate, confirmed by the site per iRECIST, the start of a new anti-cancer treatment, withdrawal of consent, pregnancy, death, or lost to follow-up. All participants will be followed by telephone for overall survival until death, withdrawal of consent, or the end of the study.
 
Upon study completion, participants may be enrolled in a pembrolizumab extension study if available.

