## 4 STUDY DESIGN

### 4.1 Overall Design

This is a randomized, cross-over, multicenter, open-label, bioavailability, and safety study of pembrolizumab in participants with advanced melanoma to be conducted in conformance with Good Clinical Practices (GCP). This Phase 1 study will be conducted in participants with unresectable or metastatic melanoma.

In Cohort A, the treatment period will continue every 21 days for up to 35 cycles (approximately 2 years). In Cohort B, the treatment period will continue every 42 days for up to 18 cycles (approximately 2 years). Treatment will continue as long as participants are receiving benefit from treatment and have not had disease progression or met any criteria for study withdrawal.

In greater detail, the study consists of:

- A screening period of up to a 28-day duration to ensure that the participant is eligible for the study.
- An intervention period of approximately 104 weeks of treatment with pembrolizumab. In Cohort A, this period will include 2 cycles of pembrolizumab administered via SC injection and 1 cycle of IV infusion over 30 minutes in a 6-sequence cross-over design. Participants will then continue with up to 32 additional cycles of pembrolizumab treatment administered by IV infusion over 30 minutes every 3 weeks. In Cohort B, participants will receive pembrolizumab via IV infusion over 30 minutes Q6W for up to 18 cycles.
- A follow-up period during which participants will be monitored for AEs for 30 days and serious adverse events (SAEs) for 90 days (30 days if the participant initiates new anticancer therapy). Participants with an ongoing AE at the time of treatment discontinuation will be followed until resolution, stabilization, the event is otherwise explained, or the participant is lost to follow-up.
- In Cohort B, participants who discontinue for reasons other than radiographic disease progression will have post-treatment follow-up imaging for disease status until disease progression is documented radiographically per RECIST 1.1 and, when clinically appropriate, confirmed by the site per iRECIST, initiating a non-study cancer treatment, withdrawing consent, becoming lost to follow-up or the end of the study. All participants will be followed by telephone for overall survival in the Survival follow-Up period until death, participant withdrawal of consent, becoming lost to follow-up or the end of the study.

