### 8.2.1.5 iRECIST Assessment of Disease

iRECIST is based on RECIST 1.1, but adapted to account for the unique tumor response seen with immunotherapeutic drugs. iRECIST will be used by the investigator to assess tumor response and progression, and make treatment decisions. When clinically stable, participants should not be discontinued until progression is confirmed by the investigator, working with local radiology, according to the rules outlined in Appendix 8. This allowance to continue treatment despite initial radiologic PD takes into account the observation that some participants can have a transient tumor flare in the first few months after the start of immunotherapy, and then experience subsequent disease response. This data will be captured in the clinical database.

Clinical stability is defined as the following:

- Absence of symptoms and signs indicating clinically significant progression of disease
- No decline in ECOG performance status
- No requirements for intensified management, including increased analgesia, radiation, or other palliative care

Any participant deemed clinically unstable should be discontinued from study intervention at the time when site-assessed first radiologic evidence of PD, and is not required to have repeat tumor imaging for confirmation of PD by iRECIST.

If the investigator decides to continue treatment, the participant may continue to receive study intervention and the tumor assessment should be repeated 4 to 8 weeks later to confirm PD by iRECIST, per investigator assessment. Images should continue to be sent in to the iCRO for potential retrospective BICR (Cohort B).

If repeat imaging does not confirm PD per iRECIST, as assessed by the investigator, and the participant continues to be clinically stable, study intervention may continue and follow the regular imaging schedule. If PD is confirmed, participants will be discontinued from study intervention.

If a participant has confirmed radiographic progression (iCPD) as defined in Appendix 8, study intervention should be discontinued; however, if the participant is achieving a clinically meaningful benefit, an exception to continue study intervention may be considered following consultation with the Sponsor. In this case, if study intervention is continued, tumor imaging should continue to be performed following the intervals as outlined in Section 8.2.1.2 and submitted to the iCRO (Cohort B).

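### Section 8.11.3.3 makes Cohort B survival follow-up conditional on confirmed progression or new therapy, against the all-participant rule in Sections 1.1 and 4.1; applied literally, it censors OS informatively

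*Combined protocol and SAP*

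**What the plan says.** Section 7.1 keeps participants who stop treatment in the study and refers to Sections 1.3 and 8.11.3 for what follows. Beyond the safety visit, 8.11.3 gives Cohort B two routes.

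- Section 8.11.3.1, imaging follow-up: "Participants who discontinue study treatment for a reason other than disease progression will move into the Follow-Up Phase".
- Section 8.11.3.3, survival follow-up by telephone about every 12 weeks: "Participants who experience confirmed disease progression or start a new anticancer therapy, will move into the Survival follow-Up Phase".

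The rule for clinically unstable participants is in Section 8.2.1.5: "Any participant deemed clinically unstable should be discontinued from study intervention at the time when site-assessed first radiologic evidence of PD". The same sentence adds that such a participant "is not required to have repeat tumor imaging for confirmation of PD by iRECIST". Table 8 leaves the repeat scan to the investigator's discretion.

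The overview sections set no such condition on survival follow-up. Section 1.1: "All participants will be followed by telephone for overall survival until death, withdrawal of consent, or the end of the study". Section 4.1: "All participants will be followed by telephone for overall survival in the Survival follow-Up period until death, participant withdrawal of consent".

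Section 8.11.4 lets the Sponsor ask for updated survival status, but does not oblige it to. Participants without a documented death are censored for OS at last follow-up (Section 9.4.3.2) or at the last known alive date (Table 12).

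**The concern.** Section 8.11.3 is the procedure that a site consults once treatment has stopped, and its two entry rules do not cover everyone. A participant whose progression was never confirmed has not stopped for a reason other than progression, and has not had confirmed progression. If no new anticancer therapy is started, no route applies.

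This group is not a random sample. Participants taken off treatment at first progression because they are clinically unstable can be expected to die sooner than the rest of the cohort. If contact with them ends, their deaths become censored times. Kaplan-Meier estimation assumes that a censored participant has the same later risk as those still followed, so the curve would be too high. Cohort B has one arm, so there is no comparator in which the same bias could cancel.

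**Working it through.** **Routes after stopping, Cohort B**

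| Situation at or after stopping | 8.11.3.1 (imaging) | 8.11.3.3 (survival) | 1.1 and 4.1 |
|---|---|---|---|
| No progression, no new therapy | yes | no | covered |
| Confirmed progression | no | yes | covered |
| New anticancer therapy started | ends | yes | covered |
| Unconfirmed radiographic progression, no new therapy | no | no | covered |

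The last row can arise in three ways: the waived scan in 8.2.1.5; Section 8.2.1.3, where the scan at discontinuation is the last one required if the investigator does not implement iRECIST; and progression during off-treatment imaging, because 8.11.3.1 ends at progression while 8.11.3.3 starts at confirmed progression.

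**What still captures a death under 8.11.3 read alone**

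- Sections 8.4.1 and 8.11.3.2 collect serious adverse events for 90 days, shortened to 30 only if new therapy starts. Section 8.4.6 makes progression that results in death reportable. So 90-day capture applies to this group.
- Section 8.11.3.2 counts the 90 days from the last administration. With 42-day cycles the last dose may precede the decision to stop by up to about 42 days, leaving 90 − 42 = 48 days after that decision.
- Table 1 shows a 90-day telephone contact for Cohort A. The legible part of Table 2 shows a 30-day safety visit for Cohort B and no 90-day contact.

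**Size, if contact is lost**

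The plan gives no OS rate, event count or expected loss to follow-up, so there is no stated figure to reproduce and every input here is an assumption. A fraction f of the cohort is in the affected group. They stop at 2.8 months plus an exponential time with mean 4 months, then survive an exponential time with median m. Everyone else has exponential survival with median 30 months. The data cut is at 36 months.

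If information ends c months after stopping, the share of the affected group alive and censored at that point is 2^(−c/m). For m = 3 this is 2^(−1/3) = 0.79 at c = 1 and 2^(−1) = 0.50 at c = 3.

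Kaplan-Meier OS in a simulated cohort of 400,000, as 12-month / 24-month percentages:

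| f | m (months) | Complete follow-up | Capture to 90 days | Contact ends at 30 days |
|---|---|---|---|---|
| 5% | 2 | 73.2 / 54.6 | 74.0 / 55.8 | 75.3 / 57.0 |
| 5% | 6 | 74.8 / 55.4 | 75.5 / 57.2 | 76.1 / 57.7 |
| 10% | 3 | 71.8 / 52.0 | 73.6 / 55.2 | 75.6 / 57.1 |
| 20% | 2 | 65.6 / 46.2 | 68.8 / 50.9 | 73.7 / 55.5 |
| 20% | 3 | 67.8 / 46.8 | 71.3 / 53.1 | 75.3 / 56.8 |
| 20% | 6 | 71.7 / 49.1 | 74.5 / 56.0 | 76.9 / 58.3 |

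Over all nine combinations of f = 5, 10, 20% and m = 2, 3, 6 months, the excess over complete follow-up is:

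- 90-day capture: 0.7 (75.5 − 74.8) to 3.5 (71.3 − 67.8) points at 12 months, and 1.2 (55.8 − 54.6) to 6.9 (56.0 − 49.1) at 24 months.
- Contact ending at 30 days: 1.3 (76.1 − 74.8) to 8.1 (73.7 − 65.6) points at 12 months, and 2.3 (57.7 − 55.4) to 10.0 (56.8 − 46.8) at 24 months.

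A second set of assumptions (100 participants, stopping at 1.5 to 6 months, f = 5, 10, 15%) gives, with 90-day capture, 1.2, 2.5 and 3.7 points at 12 months for m = 2, and 1.4, 2.9 and 4.1 for m = 3. Both sets support roughly 1 to 4 points at 12 months.

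For scale, the binomial standard error of a 12-month rate of 71.8% in 100 participants is √(0.718 × 0.282 / 100) = 4.5 points.

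**The case against.** The strongest reply is that the design, taken as a whole, already follows everyone. Sections 1.1 and 4.1 both say so, each directly after the sentence on Cohort B imaging. Table 2 in Section 1.3, which Section 7.1 names beside 8.11.3, has a 12-weekly survival follow-up column with no visible condition on entry; rows are missing from the text available here, so a relevant note may exist. Deaths are reportable to 90 days. The purpose of 8.11.4 is complete survival data at database locks, and once the Sponsor asks, participants without a scheduled contact are contacted.

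All of this stands, and it rules out two stronger readings. A reader might infer that the protocol offers these participants no survival follow-up. That is true of 8.11.3 taken alone, not of the protocol. A reader might also infer that OS will be inflated. The documents show no actual loss; the bias needs sites to apply 8.11.3.3 over 1.1 and 4.1, and the update in 8.11.4 to be absent or incomplete.

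A third inference, that participants stopped for clinical, non-radiographic progression are also missed, fails as well. Section 8.2.1.3 keeps Cohort B participants without documented progression in 12-weekly imaging, and Sections 1.1 and 4.1 exclude only radiographic progression from it.

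What the reply does not remove is the contradiction. The detailed procedure is narrower than the overview, Sections 1.1 and 4.1 give no contact interval, and the update in 8.11.4 is optional.

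**Conclusion.** The point holds as an inconsistency with a conditional consequence. Section 8.11.3.3 contradicts Sections 1.1 and 4.1 on who enters survival follow-up. Followed literally, it leaves out participants with unconfirmed radiographic progression and no new therapy.

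The direction of any bias is clear: Kaplan-Meier OS would be too high. Its size is not known from the documents. The 90-day figures are the better guide, because the plan requires that reporting for this group. The 30-day figures describe what happens if, without a scheduled later contact, those deaths are not picked up. At 12 months the 90-day excess is within about one standard error for 100 participants, but more participants would not reduce it. With complete all-participant follow-up it is zero.

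OS in Cohort B is secondary, single-arm and descriptive, with no hypothesis test. The primary response rate is unaffected. This should be corrected, but it does not threaten the main result.

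**What to change.** - **Section 8.11.3.3, Cohort B.** State that every participant no longer in treatment or imaging follow-up, including after unconfirmed radiographic progression, enters telephone survival follow-up every 12 weeks until death, withdrawal of consent or the end of the study. This matches 1.1 and 4.1.
- **Section 8.11.4, Cohort B.** Make the survival-status update required before the OS database lock.
- **Section 8.11.3.1.** Adding the word radiographic before progression would match 1.1 and 4.1. This is a harmonising edit only.

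The cost is a few sentences in an amendment, 12-weekly calls to a probably small group that Sections 1.1 and 4.1 already promise to follow, and one survival update before lock. No treatment or imaging rule changes. The edits are best made while follow-up is running, since survival status not collected then may be hard to recover.
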